### **3.3.2 Primary Efficacy Endpoint**

In order to be included in the statistical analyses of the FF-VEP data the subject had to have been evaluated using the same monitor type in both the 215ON201 and 215ON203 studies.

Subjects who were evaluated using different monitor types will have their FF-VEP data excluded from the statistical analyses. These data will appear in the subject listings.

### **Latency as determined by FF-VEP**

P100 latency value from FF-VEP is the primary efficacy outcome and will be measured for affected and fellow eyes at Day 1.

The actual value for affected eye, fellow eye and the difference between the two eyes at Day 1 will be summarized using descriptive statistics by treatment group.

Change in latency value at Day 1 for the affected eye in the current study from the baseline of fellow eye in RENEW will be analyzed using ANCOVA as mentioned in Section 3.3.1. The baseline of the fellow eye in RENEW will be used as the baseline covariate in above ANCOVA model.

#### *Sensitivity analysis*

Change in latency value at Day 1 for the affected eye in the current study from Week 32 of fellow eye in RENEW will be analyzed using ANCOVA as mentioned in Section 3.3.1. Week 32 of the fellow eye in RENEW will be used as the covariate in ANCOVA model. If Week 32 value is not available, then Week 24 value will be used to calculate the change in FF-VEP latency.

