5.6. Study Rationale

A biological effect of BIIB033 was shown in Study 215ON201 in subjects with AON. In this study, subjects received 6 doses of 100 mg/kg BIIB033 or placebo administered via IV infusion every 4 weeks up to Week 20, with Follow-Up Visits at Weeks 24 and 32. Efficacy results showed an improvement in mean change in full-field visual evoked potential (FF-VEP) latency values of the affected eye from the baseline of the fellow eye at Week 24 in the BIIB033 group compared with placebo in the intent-to-treat population (-3.48 [95% confidence interval (CI): -10.61, 3.65] msec, analysis of covariance [ANCOVA]). The treatment effect was more pronounced in the per-protocol population (-7.55 [95% CI: -15.12, 0.01] msec, ANCOVA). The electrophysiologic differences between the treatment and placebo groups, first observed at Week 12 during the dosing period, persisted throughout the subsequent monthly dosing visits.

The change in FF-VEP latency in the affected eye versus the baseline of the unaffected fellow eye by mixed model for repeated measures (MMRM) showed a greater treatment effect at Week 32 than at Week 24 for both the intent-to-treat (ITT) and per-protocol populations, despite subjects completing the dosing period at Week 20. In the ITT population, an improvement of -6.06 msec over placebo was seen in the BIIB033 group at Week 32 by MMRM ($p = 0.0711$). A significant improvement of -9.13 msec over placebo was seen in the BIIB033 group at Week 32 in the per-protocol population by MMRM ($p = 0.0112$).

Study 215ON201 also showed that all subjects, regardless of assigned treatment, recovered clinically to a large extent regardless of treatment assignment or severity of injury to the retina or the optic nerve; however, not all subjects demonstrated complete functional recovery upon electrophysiologic examination. The rationale for the discrepancy between clinical recovery and electrophysiological improvement is unclear and requires further investigation.

Given these data, the proposed follow-up study is necessary to assess the long-term electrophysiologic and clinical outcomes of this patient population with past randomized exposure to remyelinating therapy versus placebo, but also to explore potential mechanism(s) by which patients recover from previous AON. This information will be critical in the ongoing clinical development of remyelinating therapies so that they can be optimally evaluated and utilized for maximal benefit.

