#### Baseline data

Unless stated otherwise, baseline data are defined as the data collected prior to the time and/or on the date of first dose in 215ON201. If there are more than one value on or before

the date of first dose, the non-missing value closest to and prior to (including on) the date of first dose will be used as the baseline value.

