#### Analysis models

Analysis of covariance (ANCOVA) model will be used as the primary inferential analysis approach to evaluate changes from the baseline measurement in 215ON201 to Day 1 of 215ON203 in efficacy endpoints and to test the treatment differences between BIIB033 and placebo. ANCOVA model will include terms for the baseline value and treatment group. Based on Type III sum of squares, Least-squares (LS) adjusted mean of treatment difference, 95% confidence interval for the difference and the associated p-value will be presented.

Since this is a follow up study, due to loss of follow up, if the distribution of the responses is markedly non-normal (eg., highly skewed or contains outliers), the normality assumption appears dramatically violated, the Wilcoxon rank-sum test will be used to compare the treatment difference of efficacy endpoints. Normal probability plot, and QQ-plot with tests will be used to check normality assumption.

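### The Week 32 sensitivity analysis adjusts for a fellow-eye latency measured after dosing, so it removes an unknown share of any drug effect on that eye and does not estimate the change it names

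*SAP*

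**What the plan says.** The primary model in SAP 3.3.2 takes the Day 1 affected-eye latency as a change from the pre-dose fellow eye and adjusts for that pre-dose value: "The baseline of the fellow eye in RENEW will be used as the baseline covariate in above ANCOVA model". This follows the general model in SAP 3.3.1, where the "ANCOVA model will include terms for the baseline value and treatment group", and the definition in SAP 3.1, where "baseline data are defined as the data collected prior to the time and/or on the date of first dose in 215ON201" (unless stated otherwise).

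The sensitivity analysis in SAP 3.3.2 changes both roles. The change is now taken "from Week 32 of fellow eye in RENEW will be analyzed using ANCOVA as mentioned in Section 3.3.1", and "Week 32 of the fellow eye in RENEW will be used as the covariate in ANCOVA model". There is a fallback: "If Week 32 value is not available, then Week 24 value will be used to calculate the change in FF-VEP latency". No reason is given for moving the covariate to a later visit, and the text does not say whether the covariate also moves to Week 24 under the fallback.

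Protocol 5.6 gives the timing in the parent study: "subjects received 6 doses of 100 mg/kg BIIB033 or placebo administered via IV infusion every 4 weeks up to Week 20". Both visits that the sensitivity analysis draws on fall later than that last scheduled dose, since the same sentence ends "with Follow-Up Visits at Weeks 24 and 32". I read RENEW in the SAP as Study 215ON201.

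**The concern.** Week 32 is 12 weeks after the last scheduled dose (32 - 20), and Week 24 is 4 weeks after it (24 - 20). A fellow-eye latency from either visit is therefore an outcome measured after randomisation and after dosing. The drug was given intravenously, and Protocol 5 describes its aim as remyelination in the central nervous system, not in one eye. An arm difference in the fellow eye cannot be ruled out by design, and the visible text reports no fellow-eye result by arm.

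If such a difference exists, a model that adjusts for it no longer estimates the drug effect on the affected eye. The reader then cannot interpret the comparison with the primary result. Disagreement could mean that the primary finding is fragile, or only that the covariate has absorbed part of the effect. Agreement would not be a clean test of the primary model, because the two analyses target different quantities. Adjusting for the fellow eye gains precision mainly when the two eyes are correlated, which is also when the distortion can arise.

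**Working it through.** The plan states no figure for this analysis and no sample size calculation, so there is no planned number to reproduce. The check is algebra, followed by an illustration.

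**Notation.** Y is the Day 1 affected-eye latency. X is the Week 32 fellow-eye latency. b is the pooled within-arm slope of Y on X. delta_a and delta_f are the drug-minus-placebo effects on the affected and the fellow eye.

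**Step 1: the reference cancels.** The outcome is Y - X, with X as covariate. The within-arm slope of Y - X on X is b - 1. The ANCOVA treatment coefficient is the arm difference in the outcome minus that slope times the arm difference in X:

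(diff Y - diff X) - (b - 1) × diff X = diff Y - b × diff X.

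This is the coefficient from regressing Y itself on treatment and X. Subtracting X from the outcome changes only the slope, by exactly 1. In one simulated data set of 82, drawn only to check the algebra, both outcomes gave a treatment coefficient of -7.892, with slopes of -0.996 and 0.004.

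**Step 2: what is estimated.** The target is delta_a - b × delta_f.
- If b = 0, it is the affected-eye effect, delta_a.
- If b = 1, it is delta_a - delta_f, the arm difference in the stated change from Week 32.
- For other b, it is neither, unless delta_f = 0.

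**Step 3: comparison with the primary model.** There the covariate is measured before dosing, so the drug cannot have moved it and no share of a later fellow-eye effect is removed. In simulations of 400,000 subjects per setting with delta_a = -6.06 msec, the pre-dose model returned -5.99 to -6.13 msec in every setting. The Week 32 model followed the formula within 0.1 msec.

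**Step 4: illustration.** For scale, delta_a is set to -6.06 msec, the intent-to-treat difference at Week 32 in Protocol 5.6. The values of delta_f and b are assumptions; neither is in the documents. Each cell is -6.06 - b × delta_f, in msec.

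| b | delta_f = -1 | delta_f = -2 | delta_f = -3 |
|---|---|---|---|
| 0 | -6.06 | -6.06 | -6.06 |
| 0.25 | -5.81 | -5.56 | -5.31 |
| 0.5 | -5.56 | -5.06 | -4.56 |
| 0.75 | -5.31 | -4.56 | -3.81 |
| 1 | -5.06 | -4.06 | -3.06 |

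The loss is b × |delta_f|, so 0 to 3 msec. The largest loss is 3/6.06 = 49.5% of the intent-to-treat figure and 3/9.13 = 32.9% of the per-protocol figure in Protocol 5.6. SAP 3.3.1 makes the per-protocol population primary. At b = 0.5 and delta_f = -2 the loss is 1 msec: 16.5% and 11.0%. If the drug lengthened fellow-eye latency and b were positive, the estimate would move away from zero instead.

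**Step 5: the fallback.** The Week 24 value is provided for the change only. Read literally, a subject without a Week 32 value would have an outcome but no covariate, and would drop out of a complete-case ANCOVA.

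**The case against.** The strongest reply is that this is a supportive analysis with other checks around it. SAP 3.3.1 treats the intent-to-treat analyses of all efficacy endpoints as sensitivity analyses, and the intent-to-treat run of the primary model keeps the pre-dose covariate. It also provides a Wilcoxon rank-sum test if normality fails. SAP 3.3.2 adds a categorical latency analysis against the pre-dose fellow eye and summarises Day 1 fellow-eye latency by arm, which is a later but direct look at that eye. The protocol calls the fellow eye unaffected, and no drug effect on it is reported. The baseline definition also allows stated exceptions. All of this stands, and it keeps the point small. But unaffected describes disease status, not absence of drug effect, and none of these checks makes the Week 32 coefficient estimate what it is said to estimate.

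A reader might go further in four ways that the documents do not support:
- **The whole fellow-eye effect is subtracted, or subtracted twice.** Only b times the effect is removed. Using the value as both reference and covariate adds nothing, because the reference cancels.
- **This is the only sensitivity analysis of the latency endpoint.** The analyses listed above show otherwise.
- **Every subject had all six doses before the covariate was measured.** That is the schedule. SAP 3.1 requires one dose for the intent-to-treat population and allows one missed dose in the per-protocol population.
- **The sensitivity result is known to be biased.** That needs a fellow-eye effect and a non-zero slope, and the documents show neither.

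**Conclusion.** The point holds as a minor one, confined to the Week 32 sensitivity analysis. It is certain from the SAP and Protocol 5.6 that the covariate is measured after the scheduled end of dosing, and from algebra that the coefficient estimates delta_a - b × delta_f. The size is conditional: zero if the drug does not act on the fellow eye or if b = 0, and up to 3 msec under the assumed ranges. The primary analysis is untouched. What needs correcting is the target: as specified, the analysis reports neither the affected-eye effect nor the change from Week 32 that it names, except in the special cases in Step 2.

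**What to change.** Replace the covariate in the Week 32 sensitivity model with the pre-dose fellow-eye latency. What else is needed depends on the purpose:
- **If the Week 32 fellow-eye reference is kept,** label the analysis supplementary. State that it estimates the arm difference in Day 1 affected eye minus Week 32 fellow eye. It then includes any fellow-eye effect in full (delta_a - delta_f), but the target is defined and does not depend on an unknown slope. Report Week 32 fellow-eye latency by arm beside it, so that the reader can see whether delta_f matters. State how Week 24 values enter.
- **If durability since Week 32 is the aim,** analyse affected-eye change from Week 32 to Day 1 with pre-dose covariates, as a separate question. A fully durable effect would appear there as an arm difference near zero.

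Two alternatives do not help. Moving both reference and covariate to the pre-dose value repeats the primary analysis. The Day 1 inter-eye difference with pre-dose covariates would itself subtract the whole Day 1 fellow-eye effect.

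The cost is a short SAP edit, one extra descriptive table, and possibly a small loss of precision if the pre-dose fellow eye predicts Day 1 latency less well than the Week 32 value. No new data are needed, because the parent-study values are already called for.

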#### *Categorical Analyses on FF-VEP latency*

In addition, each subject's latency values will be compared between baseline fellow eye in RENEW and affected eye at Day 1 in the current study. For subjects whose baseline affected eye data in RENEW are missing or more than 3% worse (higher) than baseline fellow eye, their affected eye data at Day 1 will be checked if they are within 10% of baseline fellow eye measurements in RENEW or worse than 10% (if the affected eye data are missing, they will be treated as worse than 10%). The 10% cutoff will be used to categorize latency delay as normal/mild (less or equal to 10%) or moderate/severe (>10%). Count and percent will be summarized by treatment and chi-squared test will be conducted for treatment comparison.

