#### Analysis population

Intent-to-treat (ITT) population, per-protocol population, and safety population are defined as follows.

- *Intent-to-Treat Population*

The intent-to-treat population is defined as all randomized subjects who received at least 1 dose of study treatment (BIIB033 or placebo) in 215ON201 study, and completed at least one of the 1-day assessments in this study.

- *Per-protocol Population*

The per-protocol population is defined as subjects from the ITT population who completed the 215ON201 study, did not miss more than one dose of BIIB033 or placebo, and did not receive MS modifying therapies during study 215ON201. These subjects were included in the per-protocol population of 215ON201 study.

- *Safety population*

The safety population is defined as all subjects who received at least 1 dose of study treatment in 215ON201 and completed at least one of the 1-day assessments in this study.

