**Table 3: The overall scores of T25FW, 9HPT and PASAT 3 from Biogen 999MS005 MS COG study**

	T25FW	1/9HPT	PASAT-3
mean	4.2	0.052	45.6
SD	0.95	0.0057	11.05

The Z-score for each component is defined as below:

Timed 25-Foot Walk Z-score Calculation

The Z-score is calculated as in the following formula:

$$Z_{25\text{-foot-walk}} = (-1) \times \frac{((t_1 + t_2) / 2) - MEAN(reference)}{SD(reference)},$$

where  $t_1$  and  $t_2$  are the time (in seconds) from the two trials, and the MEAN (reference) and SD (reference) are the mean and standard deviation of the averaged time from two trials for the reference population.

If a subject is missing only one trial due to reasons other than MS related physical limitation, then the time from the non-missing trial will be used to calculate the Z-score. If both trials are missing due to reasons other than MS related physical limitation then the Z-score is regarded as missing.

If either trial is missing due to MS related physical limitation, then the subject will be given a Z-score -13.7 for T25FW.

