#### PASAT-3 Z-score Calculation

For the PASAT-3, the z-score for each subject will be calculated by subtracting the reference population's mean score from the subject's PASAT-3 score and dividing by the SD of the reference population, i.e.

$$Z_{\text{PASAT-3}} = \frac{\text{PASAT3 raw score} - \text{MEAN}(\text{reference})}{\text{SD}(\text{reference})}.$$

If a subject is missing the PASAT-3 score due to MS disease limitations, the subject will be given a Z-score calculated using a raw score of 0. If missing score is due to other reasons, then the Z-score is regarded as missing.

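### Does scoring every missing Day 1 affected-eye latency as moderate/severe delay spoil the categorical FF-VEP analysis?

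*SAP*

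**What the plan says.** The categorical analysis in SAP Section 3.3.2 compares each subject's affected-eye latency at Day 1 with the fellow-eye baseline from RENEW (the SAP's name there for Study 215ON201). It is limited to a subset: "For subjects whose baseline affected eye data in RENEW are missing or more than 3% worse (higher) than baseline fellow eye". Within that subset a delay of up to 10% is normal/mild and anything above is moderate/severe. For a missing Day 1 value the instruction is: "if the affected eye data are missing, they will be treated as worse than 10" per cent. No reason for the missing value is asked for. The analysis plan then reads: "Count and percent will be summarized by treatment and chi-squared test will be conducted for treatment comparison".

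Three other places bear on this:

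- The opening of SAP Section 3.3.2 sets a condition for entry to the FF-VEP statistical analyses: "the subject had to have been evaluated using the same monitor type in both the 215ON201 and 215ON203 studies". Data from subjects evaluated on different monitor types go to listings only.
- The ITT definition in SAP Section 3.1 requires only that the subject "completed at least one of the 1-day assessments in this study", so a subject can belong to the population without a Day 1 FF-VEP.
- SAP Appendix 2 separates reasons for the MSFC components. For the Timed 25-Foot Walk: "If both trials are missing due to reasons other than MS related physical limitation then the Z-score is regarded as missing". For PASAT-3: "If missing score is due to other reasons, then the Z-score is regarded as missing".

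**The concern.** Counting a missing latency as a bad outcome suits an eye that was tested and gave no measurable P100. It suits a noisy or failed recording less well, because nothing is then known about the eye. Scoring both alike puts non-disease failures in the moderate/severe category of both arms and pulls the two proportions together. The same SAP takes care over the reason for missingness when it scores the MSFC.

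The order of rules adds to the doubt. The missing-value rule and the monitor-type condition do not refer to each other. A programmer could blank the different-monitor data and then let the missing-value rule score them. A subject with no Day 1 FF-VEP is removed by the first sentence of the monitor condition, but is not mentioned in the second, which speaks only of subjects evaluated on different monitor types.

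At stake is the power of one chi-squared test in a study of at most 82 subjects. SAP Section 4 brings the Section 3.3.2 latency analysis into the interim as well, so the handling could affect two sets of output.

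**Working it through.** **Order of the two rules.** The monitor condition stands at the head of Section 3.3.2 and governs the subject's inclusion in the statistical analyses of FF-VEP data. The chi-squared comparison is one of those analyses. The cases sort as follows:

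| Day 1 FF-VEP | Monitor condition | Missing-value rule |
|---|---|---|
| Different monitor type | Not met; data listed only | Not reached |
| Not done | Not met on the first sentence; second sentence silent | Not reached on the plain reading |
| Same monitor, no measurable P100 | Met | Scored moderate/severe, as intended |
| Same monitor, technically inadequate | Met | Scored moderate/severe: the disputed case |

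The ITT definition does not conflict with this. It says who is in the population; the monitor condition adds a requirement for one endpoint.

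**Size of the disputed case.** The plan gives no sample size calculation, delay rate or missing-data rate for this analysis, so there is no figure to reproduce. The documents supply only the ceiling (41 + 41 = 82 dosed in 215ON201; Protocol Section 5.5.2) and the two-sided 0.05 level (SAP Section 3.1). Assumed here: 26 per arm (range 20 to 32), delay rates p1 = 25% and p2 = 60% (also 15% and 40%), and a share m of inadequate recordings, equal in both arms and unrelated to outcome.

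Under the rule the scored rate is p + (1 − p)m, so the scored difference is (p2 − p1)(1 − m). For 25% against 60%:

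- m = 5%: 28.75% against 62.0%, a difference of 33.25 points instead of 35
- m = 10%: 32.5% against 64.0%, 31.5 points
- m = 20%: 40.0% against 68.0%, 28 points

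Power comes from exact binomial enumeration of the uncorrected chi-squared test. The left-out column averages over the binomial number of usable recordings. With no missing values and 26 per arm, power is 74.0%.

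| m | Expected cases among 52 | Rule | Left out | Loss, points |
|---|---|---|---|---|
| 1% | 0.5 | 72.7% | 73.9% | 1.1 |
| 2% | 1.0 | 71.4% | 73.8% | 2.4 |
| 5% | 2.6 | 67.6% | 72.8% | 5.3 |
| 10% | 5.2 | 61.4% | 70.0% | 8.6 |
| 20% | 10.4 | 51.8% | 64.7% | 12.9 |

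(Losses are taken before rounding.) For 15% against 40% with 26 per arm, the figures at m = 5%, 10% and 20% are 48.1%, 42.0% and 31.0% under the rule, against 52.5%, 49.8% and 45.0% left out. At m = 10% with 25% against 60%, they are 49.4% against 58.7% with 20 per arm, and 75.4% against 78.7% with 32 per arm.

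**Type I error.** With 40% in both arms and m from 5% to 20%, rejection under the rule lies between 4.3% and 6.0% for 20 to 32 per arm. With nothing missing it is 4.8%, 5.3% and 5.6% for 20, 26 and 32 per arm. The spread therefore reflects mainly the discreteness of the test in small samples.

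**The case for a change.** The best case for a change is that the study is small and a few misclassified subjects can matter. Take an illustration with 8/24 against 15/24 delayed among usable recordings (p = 0.043). Scoring four further unusable recordings per arm as delayed gives 12/28 against 19/28 and p = 0.060. If the unusable recordings split six and two, p becomes 0.160 or 0.018 depending on which arm has the six. Appendix 2 shows that the sponsor accepts splitting by reason, and a sentence on order would cost little.

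The arithmetic stands, but those counts are assumed, and eight inadequate same-monitor recordings among 56 is 14%. Nothing in the documents points to such a rate. Footnote 7 of the Schedule of Activities requires sites and technicians to be approved by the central reader for FF-VEP, Protocol Section 16.3 bars a site from starting before training and technician approval, and Protocol Section 17.1.3 provides for central reading. Nor is there a reason to expect a difference by arm, since Protocol Section 9.3 withholds the 215ON201 treatment from sites and patients until the study ends.

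The Appendix 2 parallel is limited. Those rules build component Z-scores that Section 3.3.3 only summarises descriptively, and they say nothing about the denominator of a test. The FF-VEP rule also has its own consistency: a missing affected-eye value counts as impaired at RENEW baseline, where it brings the subject into the subset, and again at Day 1. Splitting by reason at Day 1 alone would break that symmetry.

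What survives is that the two paragraphs lack a cross-reference, and that the second sentence of the monitor condition is silent on tests not done.

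**Conclusion.** No change to the plan follows. The question of order is missing detail that an analyst reading Section 3.3.2 from its first sentence will settle sensibly: the monitor condition decides who enters, and the missing-value rule then acts on those who remain.

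For the technically inadequate recordings that remain, missing-as-worse is a prespecified, conservative convention. Leaving them out is not clearly better. Poor recordings may cluster in badly damaged eyes, so omitting them could bias the comparison; the power gain calculated above assumes they do not. Telling an absent P100 from an inadequate recording needs a reader's judgement that the blanket rule avoids, and the visible documents show no field for the reason.

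The cost of the rule is about 1 to 2 points of power at 1% to 2% inadequate recordings and about 5 points at 5%, with 26 per arm and 25% against 60%. Losses of 9 to 13 points need rates of 10% to 20% that the documents do not support. All of this assumes missingness that is equal by arm and unrelated to outcome. On that basis the rule dilutes a true difference and does not materially inflate type I error. It is confined to an analysis that supplements the primary ANCOVA, and the ANCOVA does not use it.
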